2. Any infants with clear evidence of bilirubin neurotoxicity on BAERs and NDI at 22-26 months (including all infants in observational analyses) will have A) moderate to increased mean and peak UB levels in combination with one or more other factors thought increase their susceptibility to bilirubin neurotoxicity; B) a lower peak TSB to UB level (as expected if albumin levels are low or bilirubin is displaced from albumin); C) will have a greater need for mechanical ventilation at 5 days than expected from baseline measures (a potential indicator of bilirubin neurotoxicity at 5 days).

Methods.

Population. Inborn infants <27 weeks' gestation by best obstetric estimate or \leq 750 g birth weight who has no major congenital anomaly or overt nonbacterial infection who has not received Intralipid and whose mother has consented to inclusion of the infant for the NRN Cycled Phototherapy Trial (which warrants higher priority based partly on stipulations in joining the NRN). Mothers of infants <27 weeks gestational age who refuse consent for this randomization control lipid trial may also be approached for consent in the observational arm of this lipid study.

Possibility of inclusion of two other major centers. With the protected time and funding provided by a KL2 award, I hope to add two centers to increase the sample size and generalizability of this pilot study. These centers are 1) the University of Alabama which generally has the largest enrollment in NRN trials and is led by [name] and 2) Stanford where [name] is Visiting Professor and [name], an international leader in studies of bilirubin and PT studies, are based. Both Drs. [name] and [name] have expressed serious interest in joining the pilot.

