3. Unbound FFA blended estimate [5ul serum] (#1)
4. Unbound FFA complete [60ul serum] (#1)
5. Unbound FFA blended estimate [5ul serum] (#2)
6. Unbound FFA complete [60ul serum] (#2)

The nurse or person obtaining blood for routine TSB levels will collect whole blood at the same time in study-provided red-top microtainer and immediately place the microtainer in a pre-

labeled amber plastic bag provided by the research team. The amber bag containing the sample will be placed in the specified location in the research refrigerator (4 degrees Celcius) as soon as feasible. A member of research team will pick up the specimen within 12 hours, transport the specimen to the UT-Houston McGovern Medical School. In the laboratory space at UT Houston McGovern Medical School, a centrifuge will be used to separate serum which will be labeled and frozen at minus 80 degrees Celsius until samples are shipped in batch to Fluoresprobe Sciences in San Diego, California.

Measurands in each whole blood sample will include concentrations of UB, albumin, total unbound free fatty acids (**uFFA**), and a uFFA profile, which includes concentrations of specific uFFA. These results will not be available with the bedside clinician and will not affect direct patient care. These will be linked with any of the following measurands from the same blood sample measured in the hospital laboratory: TSB, indirect bilirubin, direct bilirubin, albumin, triglyceride, glucose, serum bicarbonate. Additionally, if a blood gas is obtained within 4 hours of this blood draw, the pH from that blood gas will be linked to the sample, providing no intervening ventilator changes were made prior to the blood draw. Other data reflecting general status and severity of illness and/or potentially influencing UB levels will be abstracted from the medical record, including baseline variables such as sex, gestation, anthropometrics, multiple gestation, delivery information, Apgar scores, SNAP-II scores, Z scores at birth, 28 days of life, and 36 weeks postmenstrual age, etc.

Data Management. Data will be entered and stored in a secure UTH REDCap database. Paper logs of data will be secured in a locked cabinet or room.

Outcome Measures. To be compared by treatment group:

Primary outcomes:

- Area under the UB curb with UB concentration >40 nM/L
- BAER wave V latency at 34-36 weeks post menstrual age (or as soon as feasible if the infants if an artifact free BAER cannot be obtained at 34-36 weeks)

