Secondary outcomes:

- Mean UB concentration and proportion of measurements >40 nM/L, peak UB
- Peak UB concentration
- Area under the total unbound FFA (**uFFA**) concentration – time curve; mean FFAu and peak uFFA
- Peak total serum bilirubin (TSB)
- Direct bilirubin > 1.5 mg/dL before discharge
- Macronutrients prescribed (parenteral and enteral protein, fat and carbohydrate, g/kg/day)
- Weight change (g/kg/day) and Z score change from birth through day 28 and at 36 weeks postnatal age
- Relevant data abstracted from the medical record and stored in the existing databases:
 - Serial FiO₂ and ventilator settings (routinely collected generic data)
 - Bronchopulmonary dysplasia (oxygen requirement at 36 weeks PMA)
 - Perinatal and hospital acquired sepsis episodes
 - Other clinical findings potentially related to signs of or susceptibility to bilirubin neurotoxicity
 - Death or NDI as assessed at 24 months PMA
 - Death or hearing loss at 24 months PMA
 - Death or cerebral palsy at 24 months PMA

Cohort analyses (across study groups and any infants in the observational arm) Associations of interest will include:

- UB and death or NDI, unadjusted and adjusted for potential confounders
- UB and wave V latency, unadjusted and adjusted for potential confounders
- Wave V latency and death or NDI, unadjusted and adjusted for potential confounders
- uFFA measured by single probe and total uFFA measured as the sum of individual uFFA
- uFFA and UB
- Total uFFA and individual uFFA(s)

Power and Sample Size. We plan to study sufficient infants at UTH to assess BAERs in 40 infants in each treatment group and have more than 80% power at $P < 0.05$ to identify a difference between groups in wave V latency longer than 0.3 millisecond ($SD = 0.5$ millisecond). This sample size would also afford sufficient power to assess a clinically important difference in UB level.

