Data Analysis. Intention-to-treat analyses will be performed under the supervision of [name]. Generalized linear mixed models will be performed to analyze all outcomes and will include treatment group, PT type (continuous and cycled), as covariates with random effects for study site. Interaction will be assessed for treatment group and PT type. Bayesian analyses will be performed in evaluating differences in treatment effects overall and in different patient subgroups and centers. For the primary outcome and any other continuous outcome, a linear regression model will be used. Binary outcomes will be analyzed with a logistic regression and count data with a Poisson or negative binomial regression model. All priors will be neutral. For binary outcomes, all priors will be centered at RR of 1.0 (indicative of no difference between treatment groups with a 95% prior interval of 0.3-3.0 (in the log RR scale a Normal distribution with mean of 0 and variance of 0.50). A Normal (0,10²) prior will be used for the intercept term and Normal (0,1) for all other variables in the model. For the standard deviation of the center random effect, a half-Normal (0,1) prior will be used. Similar neutral informative priors (based on previous NRN PT trial⁹ where possible) will be used for non-binary outcomes. We will report posterior medians and 95% credible intervals for group differences and relative risks. We will also report posterior probability of benefit/harm for each outcome.

Similar analyses will be conducted for the cohort analyses (including infants in the observational arm).

Data Interpretation. If UB is higher and BAER wave V latency is longer in the UL than the RL group, the findings would likely prompt changes to more conservative use of Intralipid use in the

first 1-2 weeks after birth in extremely preterm infants. If values for UB and BAER wave V latency in the UL group are no higher than the RL group, the findings would support continue use of the UL regimen to provide somewhat greater caloric intake. If UB is higher with no discernible effect on wave V latency, the findings would suggest that the UB level were not high enough to cause bilirubin neurotoxicity with effects lasting to 34-36 weeks. However, findings at 2 years would need to be scrutinized for evidence of adverse neurodevelopmental effects.

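### Growth is compared as Z score change from birth, but the stated model names no birth Z score: the comparison is valid, yet less precise than the collected data allow

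*Combined protocol and SAP*

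**What the plan says.** In the combined protocol and SAP, the secondary outcomes under Outcome Measures define growth as "Weight change (g/kg/day) and Z score change from birth through day 28 and at 36 weeks postnatal age".

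The Data Analysis section then sets one model for everything: "Generalized linear mixed models will be performed to analyze all outcomes and will include treatment group, PT type (continuous and cycled), as covariates". Site enters as a random effect. For continuous outcomes it adds: "For the primary outcome and any other continuous outcome, a linear regression model will be used". No birth Z score, birth weight or gestation is named. A prior is given for "Normal (0,1) for all other variables in the model", but those variables are not listed.

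The data needed for adjustment will exist. The section on blood volume and measurements lists "Z scores at birth, 28 days of life, and 36 weeks postmenstrual age" among the items abstracted from the record. Enrollment and Randomization stratifies by site and phototherapy use only. Adjustment for confounders is mentioned only for the cohort associations, and none of those concerns growth.

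**The concern.** A change score fixes the slope of the follow-up value on the birth value at 1. If the true slope is lower, part of any chance difference between arms in birth Z score reappears, with opposite sign, as a difference in growth. Some imbalance is to be expected because size at birth is not a stratification factor. The Population section also admits two kinds of infant: "Inborn infants <27 weeks' gestation by best obstetric estimate or" a birth-weight limit of 750 g. Infants of 27 weeks or more therefore enter only by low weight, which may widen the spread of birth Z score.

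At stake is the precision of a direct measure of what halving prescribed lipid might cost nutritionally. The plan will report a posterior probability of benefit or harm for each outcome, so an avoidable shift in the growth estimate would show in a reported figure. Under Data Safety and Monitoring the plan already accepts that chance differences in birth weight and similar factors could explain an outcome difference, but it says so only for interim mortality.

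**Working it through.** **Plan's own figure.** There is none for growth. The only power statement concerns BAER wave V latency and does not enter here.

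**Inputs.** From the documents: the outcome definition, the named covariates and the extended total of 175 infants (about 87 per arm, before losses). Assumed, because the documents are silent: the SD of Z score at birth (SD0) and at follow-up (SD1), and their correlation rho. Tests are taken as two-sided at 5%.

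**Formulas.**
- Var(change) = SD0² + SD1² − 2·rho·SD0·SD1
- Var(adjusted for birth Z) = SD1²(1 − rho²)
- Slope of follow-up on birth Z: b = rho·SD1/SD0
- Difference of the two variances = (SD0 − rho·SD1)² = SD0²(1 − b)², which is zero only when b = 1
- If the change score has 80% power, adjusted power = Φ(2.802/√ratio − 1.960), where ratio is adjusted over change-score variance and 2.802 = 1.960 + 0.842

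**Equal SDs (both set to 1).** The ratio reduces to (1 + rho)/2.

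| rho | Var(change) | Var(adjusted) | ratio | 80% power becomes |
|---|---|---|---|---|
| 0.5 | 1.00 | 0.75 | 0.75 | 89.9% |
| 0.7 | 0.60 | 0.51 | 0.85 | 86.0% |
| 0.8 | 0.40 | 0.36 | 0.90 | 84.0% |
| 0.9 | 0.20 | 0.19 | 0.95 | 82.0% |

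**Unequal SDs, rho 0.4 to 0.9.**
- SD1/SD0 = 0.8: ratio 0.54 to 0.64, power 94% to 97%. At rho 0.5, for example, 0.48/0.84 = 0.571.
- SD1/SD0 = 1.2: ratio 0.82 to 1.00, power 80% to 87%. At rho 0.8, b = 0.96 and the ratio is 0.518/0.520 = 0.997, almost no gain.

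**Chance imbalance, equal SDs.** With 87 per arm the SE of the birth Z difference is √(2/87) = 0.152 SD, so its 95% range is ±0.30 SD. A one-SE imbalance moves the change contrast by (b − 1) × 0.152. At rho 0.5 that is −0.076 SD, or half of the contrast's own SE, √(2 × 1.00/87) = 0.152. With no true effect and a flat prior, the expected shift corresponds to a posterior probability of Φ(0.5) = 69% instead of 50%.

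**Is there bias?** In 10,000 simulated null trials per setting (equal SDs; rho 0.5, 0.7 and 0.9; 40 or 87 per arm), the change score had mean bias of at most 0.005 SD and type I error of 4.9% to 5.2%. In those trials where one arm started more than one SE higher, the contrast shifted on average by −0.11, −0.07 and −0.02 SD at the three correlations (87 per arm), or −0.17, −0.10 and −0.03 SD (40 per arm). After adjustment the shift was 0.01 SD or less.

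**The case against.** The strongest reply is that nothing is broken. Regression to the mean acts on both randomised arms alike, and the unadjusted interval is valid. This stands, and the simulation bears it out.

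Nor are lost power and vulnerability to imbalance two separate harms. The excess variance SD0²(1 − b)² is exactly what chance imbalance contributes, and the unadjusted interval already allows for it. This stands too, and the cost should be counted once.

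The size rests on assumptions, and the gain may be nearly nil. That is so. It limits how strongly the point can be pressed, but not whether adjustment is worth stating.

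The text also does not exclude adjustment: the models will include the named terms, and a prior is set for unnamed others. This stands in part. The other variables may be no more than phototherapy type and its interaction with treatment, so birth Z score is left unspecified rather than ruled out. An unspecified covariate can still be chosen after the data are seen.

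Finally, growth is one line in a long secondary list, with no power claim and no role in Data Interpretation or the stopping guideline. The primary outcomes are untouched. That is correct, and it keeps the point modest.

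**Conclusion.** The point holds as a missed improvement, not as an error. Baseline adjustment of the growth comparison is not pre-specified, although the birth value is collected and forms part of the outcome. With equal SDs and rho from 0.5 to 0.9, adjusting would raise 80% power to between 90% and 82%. If SD1/SD0 is 0.8 the gain is larger; if it is 1.2 with rho near 0.8 it all but vanishes. The documents cannot place the trial within this range.

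A reader might infer more, and the documents do not support it:
- That the change score biases the arm comparison or inflates type I error. Randomisation prevents both.
- That growth is the outcome most likely to show harm. The plan says only that the usual regimen gives somewhat more calories.
- That growth is the only outcome with a baseline. Serial FiO₂ and ventilator settings may also have early values.
- That the figures apply to weight change in g/kg/day. That is a weight-normalised rate, not a follow-up value minus a birth value, so neither the variance formula nor the equivalence of change and follow-up models carries over.

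**What to change.** In Data Analysis, add that the models for Z score change at day 28 and at 36 weeks include the infant's Z score at birth as a linear covariate, beside treatment group, phototherapy type and site, and that the effect reported is the adjusted difference between arms.

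With that term in a linear model, the treatment estimate is the same whether the response is the change or the follow-up Z score, since subtracting the birth value only lowers the fitted slope by 1. In the Bayesian fit, state which response is used, because a slope prior centred at zero means a different thing in each form.

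The same covariate may be added to the g/kg/day model, without claiming the gains shown here.

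The later time point should be reconciled in the same edit: the outcome list counts 36 weeks from birth, whereas the data-collection text has "SNAP-II scores, Z scores at birth, 28 days of life, and 36 weeks postmenstrual age".

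The cost is one sentence and one degree of freedom. No new data are needed. The change should be made before outcome data are examined by arm.

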I have the opportunity to enroll more patients within the limitations of my funding period, scheduled to end June 2024. I have been successful at enrolling patients at an accelerated rate from the minimum needed for adequate power. My current enrollment rate is 4-5 patients per month, and my target is 3 patients per month. The greater than anticipated enrollment rate has occurred because of the significant and unanticipated increase in the census of tiny and premature babies. By increasing our sample size, this will allow me the opportunity to ensure adequate power for an important trial, not likely to ever be repeated, and provide a more narrow confidence interval for more precise results. If differences are appreciated this would provide pilot data to motivate a larger and multicenter trial to investigate an earlier measure for neurodevelopmental impairment, allowing for earlier interventions and treatment. I propose the largest feasible enrollment for the remainder of my funding period or $n=175$ infants (Enroll an average of 5 infants per month for 11 months remaining in funding).

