Data Safety and Monitoring. [name], the study statistician, will conduct an interim analysis of mortality when half the planned sample size has been discharged from the neonatal ICU. If there is a Bayesian posterior probability >99% (assuming a neutral prior probability), the study statistician ([name]), will notify the [name], Medical Director of the CMHH Neonatal ICU and the Director of the Neonatology Division. Unless there are important chance differences between treatment groups in baseline risk factors that are known to influence outcomes of extremely premature infants (birth weight, gestational age, sex, multiple births (twins, triplets), antenatal steroids, high ventilator settings) and that could account for differences in outcome, she would contact [name]. They would decide whether to halt enrollment in the study.

Predischarge outcome date will of course be entered into the study database for each infant once he/she is discharged from the NICU. The rationale for the stopping guideline is that impairment is likely to be a persisting problem and that other neonatal outcomes short of death (IVH, NEC, BPD) are short term outcomes less important than impairment or death. Were we performing frequentist analysis, the stopping guideline would be based on a $p < 0.01$ (two-tailed).

References

¹ Hay WW. Aggressive nutrition of the preterm infant. *Curr Pediatr Rep* 2013;1:doi:10.1007/s40124-013-0026-4.

² Simmer K, Rao SC. Early introduction of lipids to parenterally-fed preterm infants. *Cochrane Database Syst Rev*. 2005 Apr 18;(2):CD005256.

³ Effect of free fatty acids on bilirubin-albumin binding affinity and unbound bilirubin in premature infants. Amin SB. *JPEN J Parenter Enteral Nutr*. 2010 Jul-Aug;34(4):414-20

⁴ Hegyi T, Kleinfeld A, Huber A, Weinberger B, Memon N, Shih WJ, Carayannopoulos M, Oh W. Effects of Soybean Lipid Infusion on Unbound Free Fatty Acids and Unbound Bilirubin in Preterm Infants. *J Pediatr*. 2017 May;184:45-50

⁵ Amin SB, Maisels MJ, Watchko JF. Early Lipid Infusions and Unbound Bilirubin in Preterm Neonates: A Cause for Concern?. *J Pediatr*. 2017 May;184:6-7

⁶ Shapiro SM, Popelka GR. Auditory impairment in infants at risk for bilirubin-induced neurologic dysfunction. *Semin Perinatol*. 2011;35(3):162-170.

⁷ Wennberg RP, Ahlfors CE, Bickers R, McMurry CA, Shetter JL. Abnormal auditory brainstem response in a newborn infant with hyperbilirubinemia: improvement with exchange transfusion. *J Pediatr*. 1982;100(4):624-626.

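### The stated power of more than 80% for BAER wave V latency is about 75% on a two-sided 5% test; with the printed inputs, only an undeclared one-sided test exceeds 80%

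*Combined protocol and SAP*

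**What the plan says.** The Power and Sample Size section states that the study will "assess BAERs in 40 infants in each treatment group and have more than 80% power" at P < 0.05. The target is a "difference between groups in wave V latency longer than 0.3 millisecond", with an SD of 0.5 ms. Sidedness is not given there, nor anywhere else for this calculation. The only mention of sidedness in the document is in Data Safety and Monitoring, where two-tailed describes the frequentist counterpart of the mortality stopping guideline, which is a different rule.

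The same section then raises enrolment: "By increasing our sample size, this will allow me the opportunity to ensure adequate power", and "I propose the largest feasible enrollment for the remainder of my funding period", put at 175 infants. It gives no power figure for 175. It also does not say how many of the 175 will be randomised, or how many are expected to have a usable BAER.

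Outcome Measures lists wave V latency as one of two primary outcomes.

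**The concern.** All the inputs to the power statement are printed, so it can be checked directly. With a standardised difference of 0.6 and 40 per group, a conventional two-sided 5% comparison falls below 80%.

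The figure matters because the investigators say in the rationale that they expect no BAER difference between groups, and Data Interpretation draws conclusions from finding no effect on wave V latency. The weight that such a result can carry depends on the chance of missing a true difference. At 40 per group and two-sided 5%, that chance for a true 0.3 ms difference is about 24.5% (100 − 75.5), where the plan implies less than 20%.

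**Working it through.** **Inputs** (all from Power and Sample Size)
- n = 40 per group. These are infants with a BAER assessed, so no dropout allowance is needed.
- Difference 0.3 ms, SD 0.5 ms, so d = 0.3 / 0.5 = 0.6.
- Significance level 0.05, sidedness not stated.

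**Method.** Two-sample t test with equal groups. The noncentrality is d × √(n/2) = 0.6 × √20 = 2.683, with 2 × 40 − 2 = 78 degrees of freedom. Power is the probability that a noncentral t with these parameters exceeds the critical value. The normal approximation is Φ(2.683 − z).

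**Which reading gives the plan's figure?**

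| Test at 5%, 40 per group | Critical t (78 df) | Power, t test | Power, normal approximation |
|---|---|---|---|
| One-sided | 1.665 | 84.5% | Φ(2.683 − 1.645) = Φ(1.038) = 85.0% |
| Two-sided | 1.991 | 75.5% | Φ(2.683 − 1.960) = Φ(0.723) = 76.5% |

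The claim of more than 80% is met one-sided. Two-sided, it is missed by 4.5 points (t test) or 3.5 points (normal approximation).

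**Number needed for 80%, two-sided.** By t test, 44 per group give 79.5% and 45 give 80.4%. The plan is therefore 5 BAERs per group short. The normal approximation gives 44 per group.

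**Could rounding of the inputs explain it?** Two-sided, 40 per group, t test:

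| Difference (ms) | SD (ms) | Power |
|---|---|---|
| 0.30 | 0.47 | 80.5% |
| 0.30 | 0.50 | 75.5% |
| 0.30 | 0.54 | 68.9% |
| 0.32 | 0.50 | 80.7% |

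The 80% line falls at an SD of about 0.473 ms (difference 0.3 ms), or at a difference of about 0.317 ms (SD 0.5 ms). Values hidden by rounding could move the figure either way.

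**Power at the current target of 175.** Assume that all 175 are randomised 1:1 and that a fraction f has a usable BAER. The number per group is then 175 × f / 2. The document gives no value for f. Two-sided 5%, t test:

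| f | BAERs per group | Power for 0.3 ms |
|---|---|---|
| 0.50 | 43.75 | 79% |
| 0.75 | 65.6 | 93% |
| 1.00 | 87.5 | 98% |

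Two groups of 45 make 90 BAERs, and 90 / 175 = 51%.

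**The case against.** The strongest reply is that the figure is under-specified, not miscalculated. It does reproduce on a one-sided 5% test, and Data Interpretation is partly directional: it acts if "BAER wave V latency is longer in the UL than the RL group". The one two-tailed statement belongs to the stopping guideline and does not settle the matter. This stands as a possibility, and only the authors know which calculation was run. But a difference between groups at P < 0.05, with nothing further said, reads as two-sided. A one-sided calculation has to be declared for a reader to tell 75% from 84%.

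Three further routes to 80% exist, each needing a value that the plan does not print:
- **Unrounded inputs.** An SD near 0.47 ms would suffice, but one near 0.54 ms makes the shortfall worse.
- **A larger effect.** Latency differences longer than 0.3 ms could be read to include 0.32 ms, but 0.3 ms is the only planning value given.
- **Covariate adjustment.** The planned model includes phototherapy type. Covariates would have to explain a little over 10% of the variance (10% gives 79.8%, 11.7% gives 80.5%), and the power statement claims no such gain.

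The planned Bayesian analyses do not change this, because the claim is framed as frequentist power at P < 0.05.

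The last objection is that the 175 target overtakes the issue. That holds for the consequence: nothing here shows the enlarged trial to be underpowered. It does not correct the sentence, which remains current text and is the baseline against which the increase is justified.

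**Conclusion.** The concern holds. With the inputs as printed, 40 BAERs per group give 75.5% power on a two-sided 5% t test, about 5 points below the stated minimum, and 45 per group are needed for 80%. The claim is true only on a one-sided 5% test (84.5%), which the plan does not declare. The conclusion rests on reading the comparison as two-sided, taking 0.3 and 0.5 ms at face value, and assuming no variance reduction from covariates.

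The shortfall is in the reported figure, not in the trial's present capacity. Roughly half of the 175 infants with usable BAERs would be enough for 80%, provided that all 175 are randomised 1:1.

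**What to change.** In Power and Sample Size, replace the power clause with wording such as: *40 BAERs per group give about 75% power (two-sided 0.05) for a 0.3 ms difference (SD 0.5 ms); 45 per group are needed for 80%.* If a one-sided 5% test was used, say so and give about 84%. If unrounded inputs were used, print them and the power that follows.

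A useful but optional addition, where the section raises enrolment to 175, is the two-sided power for 0.3 ms at that target, with the assumed number randomised and the assumed number with a BAER. At least 90 BAERs among randomised infants, split 1:1, would support a statement of 80% or more.

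The cost is a change of wording in one section. Enrolment, analysis and decision rules stay as they are. Either one reported figure becomes slightly less favourable, or an assumption already made becomes visible.

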Enrollment and Randomization. Patients will be approached for informed consent after informed consent has been given or refused for the NRN Cycled PT Trial. Infants for whom informed consent is obtained for this lipid study will be randomized using a variable block size stratified by study site and phototherapy use (continuous or cycled which may affect UB level) to either UL or RL using a web-based computerized program (REDCap). Lipid and phototherapy use are concurrent. Mothers who refuse consent infants for this lipid trial will be asked if they would consent for their infant to be included in the observational component of this study so that UB levels can be related to BAERs and 2-year outcomes. In the observational component Intralipid infusions will be at the attending physician's discretion and care would be altered only by collection of the small amount of blood (\leq 2 mL total) as for participants randomized to UL or RL.

Treatment Regimen.

UL regimen: Intralipid will be started at 1 g/kg/day and routinely advanced by 1 g/kg/day each day to a max of 3 g/kg/day as per usual clinical practice.

RL regimen: Intralipid will be started at 0.5 g/kg/day and routinely advanced by 0.5 g/kg/day each day to a max of 1.5 g/kg/day (half rate of usual clinical practice).

The assigned treatment regimen (UL or RL) will remain in effect for a minimum of 7 days and a maximum of 14. On postnatal day 8-14, the Intralipid preparation and dosage maybe changed at the discretion of the clinical team if phototherapy has been off for \geq 48 hours (TSB <5 mg/dL). (After that point, the Intralipid preparation and dosage maybe changed at the discretion of the clinical team). Throughout the study period, the infusion rates for both regimens may be decreased, and advances may be delayed for reason of lipid intolerance providing the justification is documented in the daily progress note. (Each study site should strive to standardize criteria for lipid intolerance so as to minimize the likelihood of using different criteria for the treatment groups). Intralipid infusions will be routinely initiated on specified day after the birthday as per the routine in the study site; this will be the first day after the birthday in Houston. The dates and times of start, stop, and changes in infusion rates will be recorded.

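### The randomised-comparison models leave out gestational age and birth weight, which are already collected; the comparison stays valid, but UB area and wave V latency may be estimated less precisely than they could be.

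*Combined protocol and SAP*

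**What the plan says.** The Data Analysis section sets one specification for all outcomes: the models "will include treatment group, PT type (continuous and cycled), as covariates with random effects for study site". It adds an assessment of the treatment-by-phototherapy (PT) interaction, and linear regression for continuous outcomes. A general prior is stated for the remaining model variables, but no further variable is named.

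The named terms follow the design. Under Enrollment and Randomization, infants are "randomized using a variable block size stratified by study site and phototherapy use". Neither gestational age nor birth weight is a stratification factor.

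Both variables appear elsewhere in the document:

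- **Population:** eligibility is set by "gestation by best obstetric estimate or" a birth-weight limit, so both should be known for every infant.
- **Study Assessments:** data reflecting general status and severity of illness, or "potentially influencing UB levels will be abstracted from the medical record, including baseline variables such as sex, gestation, anthropometrics", are collected.
- **Data Safety and Monitoring:** at the interim mortality look, chance imbalance is to be considered in "baseline risk factors that are known to influence outcomes of extremely premature infants (birth weight, gestational age, sex" and further factors.

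Adjusted estimates are planned only for the cohort associations, for example "UB and wave V latency, unadjusted and adjusted for potential confounders". Those confounders are not listed.

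**The concern.** Because treatment is randomised, a linear model without gestational age and birth weight still estimates the mean difference without bias. The question is efficiency. If the two variables explain part of the variation in an outcome, leaving them out keeps that part in the residual error and widens the interval.

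This bears on the trial's stated aims. Power and Sample Size gives a narrower confidence interval as one reason for enlarging enrolment to 175. The rationale expects similar BAERs in the two arms, and Data Interpretation would draw a conclusion from finding no discernible wave V effect. Such a result is only as persuasive as its interval is narrow. Two baseline values already held serve the same purpose without another infant.

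**Working it through.** **Inputs from Power and Sample Size.** Wave V difference 0.3 ms, SD 0.5 ms, 40 infants per group with a BAER, enlarged enrolment 175.

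**Assumptions.** Two-sided 5% level (the plan does not state the sidedness). R² is the share of outcome variance explained by gestational age and birth weight together beyond PT type and site; values 0 to 0.30 are tried. Three sizes are used:

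- 40 per arm, as stated.
- 65 per arm, if about 25% of 175 lack a BAER (an assumption).
- 87 per arm, an upper bound, since the 175 may include observational infants or infants without a BAER.

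**The plan's own figure.** At 40 per arm, SE = 0.5 × √(2/40) = 0.1118 ms. Two-sided power for 0.3 ms is 75.5% (noncentral t) or 76.5% (normal approximation). The stated figure of more than 80% is reproduced only with a one-sided 5% test (85.0%, normal). That is a separate matter and this point does not depend on it.

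**Formulas, with N the total in both arms and n = N/2.**

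- Unadjusted half-width = t(0.975, N−2) × 0.5 × √(2/n).
- Adjusted half-width = t(0.975, N−4) × 0.5 × √(1−R²) × √(2/n) × √[(N−3)/(N−5)].

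The last factor is the expected cost of chance imbalance in two estimated covariates, so the adjusted figures are net of that cost.

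**Worked example, 87 per arm, R² = 0.10.** Unadjusted: 1.974 × 0.5 × √(2/87) = 1.974 × 0.0758 = 0.150 ms. Adjusted: 1.974 × 0.0758 × √0.90 × √(171/169) = 0.143 ms, which is 4.6% narrower.

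**95% half-width for wave V latency (ms)**

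| Per arm | Unadjusted | R² 0 | 0.05 | 0.10 | 0.20 | 0.30 |
|---|---|---|---|---|---|---|
| 40 | 0.223 | 0.226 | 0.220 | 0.214 | 0.202 | 0.189 |
| 65 | 0.174 | 0.175 | 0.171 | 0.166 | 0.156 | 0.146 |
| 87 | 0.150 | 0.151 | 0.147 | 0.143 | 0.135 | 0.126 |

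At 40 per arm the change is 1.4% wider, then 1.2%, 3.8%, 9.3% and 15.2% narrower. At 87 per arm it is 0.6% wider, then about 2%, 4.6%, 10.0% and 15.8% narrower. A simulation with 8,000 runs and covariates correlated 0.6 gave the same percentages to within about 0.1 point.

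**Power for 0.3 ms.** At 40 per arm: 75.5% unadjusted; 74.4%, 76.5%, 78.7%, 83.2% and 87.8% adjusted, so 80% needs R² of about 0.13. At 87 per arm power is already 97.6% unadjusted, and the gain is interval width only.

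**Break-even R².** Setting the two half-widths equal gives 0.027 at N = 80, 0.016 at 130 and 0.012 at 174.

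**Equivalent infants.** The unadjusted N that matches the adjusted half-width at N = 174 is 172, 181, 191, 214 and 245 across the five R² values: −2, +7, +17, +40 and +71 infants.

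**UB area.** The document gives no SD, so no absolute figure is possible. The same percentages apply at the same R², approximately if the area is skewed or has many zeros.

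**Prior scale.** With a standardised covariate and a Normal(0,1) prior, the share of its coefficient kept is about N/(N + residual variance). At N = 174 and R² = 0.10:

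- wave V: 174/(174 + 0.225) = 0.999;
- UB area with an assumed SD of 10 units: 174/(174 + 90) = 0.66;
- UB area with an assumed SD of 50 units: 174/(174 + 2250) = 0.07;
- prior SD equal to the outcome SD: 174/(174 + 0.9) = 0.995.

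A unit-scale prior carried over to an outcome in large units could therefore cancel the gain.

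All of these are frequentist approximations to the planned Bayesian intervals.

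**The case against.** The planned model is not wrong. It is unbiased and reflects the stratification, and a longer covariate list is a design preference. That is correct, and no claim of invalidity is made.

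The benefit rests on an R² that the document does not give, and below break-even the interval widens slightly. The textual support is also indirect. The Data Safety and Monitoring list serves the mortality review and speaks of outcomes in general. The Study Assessments sentence covers severity of illness as well as influence on UB, so it does not assert that gestation affects UB. For wave V the link may be weak, because eligibility is narrow and the endpoint is "BAER wave V latency at 34-36 weeks post menstrual age" whatever the gestation at birth. These points stand, and the wave V gain may be nil. The trade is still lopsided: at most 1.4% wider, against 4% to 5% narrower at R² = 0.10.

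The effect is small in absolute terms at the enlarged size: R² of 0.05 to 0.10 takes 0.003 to 0.007 ms off the half-width. This also stands, and it is why the point is a low-cost improvement and not a defect.

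Finally, the document describes no blinding of BAER results or of the analyst to arm, so an amendment before outcomes are seen by arm may not be attainable for wave V. That limits when the change can be made, not whether it is sound.

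**Conclusion.** The point holds as a low-cost improvement. The randomised comparison is valid as planned. It may give up precision for UB area and wave V latency by omitting two baseline variables that define eligibility and are already collected.

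At the upper bound of 87 per arm, adjustment changes the wave V interval by between 0.6% wider and 15.8% narrower over R² from 0 to 0.30. It helps once R² exceeds about 0.012 (0.027 at 40 per arm). The size of the gain is unknown because R² is assumed throughout. The larger R² values are illustrations, and the document supports none of them in particular. Confidence is medium.

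**What to change.** Make a dated amendment before anyone with a say in the analysis has seen the relevant outcomes by arm:

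1. Add gestational age and birth weight, each centred and divided by its SD, as continuous covariates in the models for the two continuous primary outcomes.
2. State covariate priors on each outcome's own scale, for example a prior SD equal to the outcome SD pooled over arms. The plan now says only that priors for non-binary outcomes will be similar and neutral.
3. Keep the model with PT type and site only as a sensitivity analysis.
4. If outcomes by arm have already been seen, label the adjusted result supplementary. If the covariates are left out on purpose, say why.

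Extension to binary outcomes is optional. In a logistic model adjustment changes the quantity estimated, so results would need to be standardised to relative risks. Extend to mortality only if the interim look has not taken place; otherwise call the adjusted mortality result supplementary. The statistician "will conduct an interim analysis of mortality when half the planned sample size has been discharged from the neonatal ICU". Enrolment so far is about 175 − 5 × 11 = 120 infants. Half of 175 is about 88 discharges. Half of 80 is 40, a lower bound because the 80 counts infants with a BAER and not all those enrolled. The look may therefore already have happened; the document does not say.

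For the two primary outcomes the cost is an amendment, two parameters and a stated prior scale, with no new data. It is higher for the binary outcomes.
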